**Date: April 22, 2026**

## **Study Protocol**

### **1. Background:**

Inflammatory bowel disease (IBD), including ulcerative colitis (UC) and Crohn's disease (CD), affects over 2 million people worldwide [1]. Although biological therapies have significantly improved the treatment outcomes for UC, nearly two-thirds of patients experience diminishing drug responses over time, making it crucial to explore novel therapeutic approaches targeting the underlying pathophysiology of UC. UC is associated with alterations in gut microbiota, reduced microbial diversity, and changes in the relative abundance of dominant bacterial populations. Specifically, UC patients exhibit a marked decrease in gut microbiota diversity at the species level, with a reduction in *Firmicutes* (e.g., *Clostridium butyricum*) and an increase in *Actinobacteria*, *Proteobacteria* (e.g., *Escherichia coli*), *Enterobacteriaceae*, *Streptococcus*, and *Bacteroides* [2]. Given the association between gut microbiota alterations and IBD activity, several studies [3-5] have proposed microbiota-based therapies, particularly fecal microbiota transplantation (FMT), as a treatment for UC.

FMT involves the infusion of fecal material from healthy donors into patients to restore gut microbiota balance. It is currently recognized as an effective treatment for recurrent or refractory *Clostridium difficile* infections [6,7]. Numerous studies suggest that FMT, as a therapeutic tool to regulate gut microbial homeostasis, holds potential in treating UC and other diseases, although the biochemical and/or immune mechanisms underlying its effects remain unclear [8,9]. Paramsothy et al. [10] demonstrated the efficacy of autologous FMT compared to placebo, utilizing a protocol involving colonoscopy-guided FMT followed by daily enemas for 5 days per week over 8 weeks. However, the high financial burden of this approach limits its broader clinical application. Another study [11] revealed that donor FMT prepared anaerobically for 1-week treatment led to a higher likelihood of remission at 8 weeks compared to autologous FMT. Further research is needed to assess its safety and maintain long-term remission rates.

Our team's high-quality research findings indicate that the gut microbiota of populations in Yunnan's ethnic minority regions exhibits significantly higher diversity and regional specificity compared to urban populations. This has potential value in enhancing FMT efficacy. Previous studies [12] revealed ethnic and regional differences in IBD prevalence in Yunnan Province, with lower rates among the Dai, Bai, and Miao ethnic groups compared to the Han population. An analysis of contributing factors highlighted the protective role of traditional ethnic diets, which increase gut microbial and viral diversity and probiotics content, thereby reducing UC prevalence. Based on this, the differences between donors in FMT may affect treatment outcomes, emphasizing the importance of identifying "high-quality" donors who maximize efficacy and minimize adverse reactions.

### **2. Objectives:**

To investigate the impact of different donors (Han and Bai ethnic donors) on the efficacy of FMT in treating UC and identify "high-quality" donors.

To isolate and culture key bacterial strains from Bai ethnic donors that contribute to their therapeutic effect.

### **3. Results:**

1.Primary Outcome: The primary outcome is a composite of steroid-free clinical remission

together with endoscopic remission or response at week 12, defined as a total Mayo score of  $\leq 2$  points with no individual sub-score  $>1$  point, and at least a 1 point reduction from baseline in the endoscopy sub-score (MES).

## 2. Secondary Outcomes:

① Steroid-free clinical remission ( defined as a total Mayo score of  $\leq 2$  points with no individual sub-score  $>1$  point )

② Steroid-free clinical response ( defined as a reduction of 3 points or more on the Mayo score, a 50% or greater reduction from baseline in combined rectal bleeding plus stool frequency Mayo sub-scores, or both )

③ Steroid-free endoscopic response ( defined as a Mayo endoscopy sub-score of 1 or less, with a reduction of at least 1 point from baseline )

④ Variations in fecal microbiota composition, function, and metabolites at weeks 0, 1, 8, and 12 within each group (Han donor group and Bai donor group)

⑤ Duration of microbiota recovery from baseline across weeks 0, 1, 8, and 12 within groups.

⑥ Intergroup differences in recipients' microbiota composition between the Han and Bai donor groups.

⑦ Proportional contributions of recipient, donor, or mixed-origin microbiota in FMT recipients.

⑧ Dominant bacterial strains in highly effective cases of FMT treatment.

## 4. Methods:

**1. Study Design:** This is a patient single-blind, single-center, randomized, parallel-group pilot clinical trial without placebo control. Patients will be randomized to either the Han donor or the Bai donor and followed up for a 12-week period. Subjects will undergo follow-up assessments for up to 12 weeks in accordance with the same schedule as the blinded phase (i.e., FMT administration at baseline, weekly telephone follow-up at week 1, 8, and on-site follow-up visits at week 12). Subjects who are randomized to the FMT arm or who do not wish to enter the open-label phase will be deemed to have completed the study, and no further follow-up will be arranged.

Note: Single-center means all experimental activities are conducted at the same location.

## 2. Study Population:

Participants will be recruited through press conferences, advertisements, online social media platforms, health seminars, university campuses, public transportation stations, and clinics. Subordinates, students, or employees must input their respective institutional affiliations. Only participants with adequate time to complete the consent process and deliberate on participation will be enrolled. Participants voluntarily decide to participate without coercion from investigators. Non-participation will not impact employment or academic status.

### Inclusion Criteria:

(1) Age between 14 and 79 years (inclusive), any gender.

(2) Diagnosed with ulcerative colitis (UC) per established clinical, endoscopic, and histological standards, with a disease duration of over 3 months.

(3) Active mild-to-moderate UC, defined by a Mayo score of 4 – 10, including an endoscopic score  $\geq 1$  and a physician's global assessment score  $\leq 2$ .

(4) Stable baseline medication consisting of 5-aminosalicylic acid (mesalamine).

(5) Signed written informed consent.

### Exclusion Criteria:

- (1) Participants unable to provide informed consent, answer questionnaires, or supply samples.
- (2) Pregnant women or those attempting to conceive.
- (3) Participants unwilling to use effective contraception throughout the study.
- (4) Participants deemed in remission by investigators.
- (5) Evidence or history of toxic megacolon.
- (6) Isolated rectal inflammation (<5 cm in extent).
- (7) Diagnosed with Crohn's disease or indeterminate colitis.
- (8) Participants with perianal diseases (e.g., fistulae, anal fissures).
- (9) History of significant gastrointestinal surgery (e.g., colectomy) :
  - Minor surgeries will be reviewed case by case.
  - Patients with appendectomy within 3 months will be excluded.
- (10) Antibiotic use within the past 4 weeks for any reason, including for UC.
- (11) Steroid dependence requiring >20 mg prednisone or >9 mg budesonide daily at enrollment.
- (12) Recent or anticipated usage of prohibited drugs during the study period, including:
  - Rectal corticosteroids within 2 weeks prior to the first FMT.
  - Biologics (e.g., infliximab, adalimumab, vedolizumab) within 4 weeks prior to the first FMT.
  - Other major immunosuppressants (e.g., calcineurin inhibitors, antitumor drugs) within 12 weeks prior to treatment.
  - Probiotics within 4 weeks before the first FMT.
  - Experimental drugs or protocols within 12 weeks before the first FMT.
  - Anti-tuberculosis (TB or MAC) treatment within 4 weeks before the first FMT.

#### Permitted Medications:

Participants may continue using the following medications if doses are stable within specified timeframes before the first FMT:

- Oral 5-aminosalicylic acid (stable for 4 weeks).
- Azathioprine and methotrexate ( $\geq 90$  days of use with stable doses for 4 weeks).
- Oral prednisone ( $\leq 20$  mg/day, stable for 2 weeks, gradually tapered at a rate of 2.5 mg/week to discontinue by week 8).

Subjects should maintain the same doses of oral 5-aminosalicylates, thiopurines, and methotrexate during the study. For oral prednisolone, the dose had to be tapered off gradually, at a rate of 2.5mg per week, so that subjects were no longer exposed to steroids until week 8.

#### Prohibited Medications:

- Rectal corticosteroids (2 weeks before and throughout the study).
- Antibiotics, antifungals, antivirals, probiotics, or prebiotics (4 weeks before and throughout the study).
- Biologics or calcineurin inhibitors (12 weeks before and throughout the study).

Participants using prohibited medications during the study will remain enrolled, and outcomes will still be evaluated. All prohibited medication usage will be recorded.

### 3. Fecal Donor Recruitment

#### Inclusion Criteria:

- (1) Age between 12 and 45 years (inclusive), any gender.

(2) Body Mass Index (BMI) >18 and <25.

(3) Written informed consent provided.

Exclusion Criteria:

Fecal Donation:

(1) Individuals permanently disqualified from donating feces in other studies.

(2) Individuals meeting any of the following criteria.

Social Behavior:

(3) Current or past smokers.

(4) Current heavy alcohol consumers.

Diet:

(5) Currently adhering to a strict vegan diet.

(6) Use of probiotic supplements in the past two months.

Occupation:

(7) Occupations with high risk of blood-borne diseases.

Travel History:

(8) Resided for at least six months in countries at high risk for Creutzfeldt-Jakob disease between 1980 and 1996.

(9) Traveled to areas with a high incidence of infectious diseases in the past six months.

Medical History:

(10) History or presence of HIV, HTLV, hepatitis B or C, or other known infections.

(11) History or presence of tuberculosis.

(12) History of autoimmune diseases (e.g., connective tissue diseases, thyroid disorders, inflammatory arthritis, psoriasis, alopecia).

(13) History of or concurrent atopic diseases (e.g., asthma, atopic dermatitis, eczema, eosinophilic gastrointestinal diseases).

(14) History of cardiovascular or metabolic diseases (e.g., diabetes, hypertension, hyperlipidemia, hyperglycemia, heart disease, neurological disorders, fibromyalgia).

(15) History of or concurrent neurological diseases (e.g., multiple sclerosis, Parkinson's disease, Alzheimer's disease, dementia).

(16) History of chronic pain or chronic pain syndromes (e.g., chronic fatigue syndrome, fibromyalgia).

(17) History of or concurrent cancer.

(18) Clinically diagnosed psychiatric disorders or concurrent mental illnesses (e.g., depression, bipolar disorder, schizophrenia, eating disorders).

(19) History of congenital or chronic liver diseases.

Gastrointestinal Disorders:

(20) History of or concurrent celiac disease.

(21) History of or concurrent inflammatory bowel disease (IBD).

(22) History of or concurrent irritable bowel syndrome (IBS).

(23) History of idiopathic chronic constipation or chronic diarrhea.

(24) History of gastrointestinal malignancies or polyps.

(25) History of rectal bleeding or concurrent rectal bleeding.

Medication Use:

(26) History of using major immunosuppressants (e.g., calcineurin inhibitors, exogenous

corticosteroids, biologics, anti-tumor necrosis factor agents, systemic chemotherapy).

- (27) History of growth hormone therapy.
- (28) Use of antibiotics within the past two months.
- (29) Participation in experimental drug or vaccine trials within the past two months.
- (30) Vaccination within the past month.
- (31) Use of proton pump inhibitors (PPIs) in the past two months.

Illegal Drug Use or Substance Abuse:

- (32) Intravenous drug use without a clinical prescription.
- (33) Use of illegal drugs.
- (34) Use of recreational drugs.

Risky Sexual Behavior:

- (35) Engagement in sex work.
- (36) Sexual contact with sex workers.
- (37) Anonymous sexual encounters in the past 12 months.
- (38) Sexual contact with intravenous drug users in the past 12 months.
- (39) Sexual contact with men who have had sexual contact with other men in the past 12 months.
- (40) Male-to-male sexual behavior in the past 12 months.
- (41) History of sexually transmitted infections in the past 12 months.
- (42) Sexual contact with individuals confirmed to have HIV, HTLV, hepatitis, or syphilis in the past 12 months.

Other Behavior:

- (43) Previous imprisonment or detention in the past six months.
- (44) Tattoos or body piercings performed in the past six months.

Surgical History:

- (45) History of gastrointestinal surgery.
- (46) History of any organ transplantation (e.g., solid organ, bone marrow, cornea).

Family History:

- (47) First-degree relatives with IBD.
- (48) First-degree relatives diagnosed with colorectal cancer before age.

Screening Tests:

- (49) Abnormalities in any of the following screening tests:
  - Blood Tests: Complete blood count (CBC), biochemistry, ESR, CRP, hepatitis panel, HIV, syphilis, immunoglobulins and complement, T-SPOT, Torch 5, ANA/ANCA, EB DNA, and EB composite antibodies.
  - Stool Tests: Routine analysis, occult blood, parasites, worms (tapeworm, roundworm, hookworm, whipworm), schistosomes, Salmonella, Shigella, Clostridioides difficile (CDI), Helicobacter pylori (HP), and resistant bacteria (MDRA, MRSA, ESBL, CRE, VRE).
  - Urine Tests: Routine urinalysis and pregnancy test (if applicable for females).

Potential fecal donors will be recruited from the general population. Candidates will complete an interview and screening questionnaire, followed by laboratory testing. Fecal samples will be collected only from donors who meet all eligibility criteria.

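### The plan bars donors with HTLV but lists no HTLV test; a lesser point is that it describes no step to confirm donor eligibility at donation

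*Combined protocol and SAP*

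**What the plan says.** Everything here is in section 4, Methods, under Fecal Donor Recruitment, unless stated otherwise.

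- **HTLV exclusion.** Donor criterion 10 excludes "History or presence of HIV, HTLV, hepatitis B or C, or other known infections". Criterion 42 names HTLV again, as sexual contact within 12 months with a person confirmed to have it.
- **Tests.** Criterion 49 lists the blood, stool and urine tests whose abnormality excludes a donor. The infection-related blood tests are a hepatitis panel, HIV, syphilis, T-SPOT, Torch 5 and Epstein-Barr markers. HTLV is not named in any of the three lists.
- **Sequence.** "Candidates will complete an interview and screening questionnaire, followed by laboratory testing". The next sentence is the collection rule: "Fecal samples will be collected only from donors who meet all eligibility criteria".
- **Look-back criteria.** Several donor exclusions run over a recent period, for example "Use of probiotic supplements in the past two months", "Traveled to areas with a high incidence of infectious diseases in the past six months" and "Use of antibiotics within the past two months". None names the date from which the period is counted.
- **Recipients.** Section 5 gives each recipient three infusions of fresh material. Permitted Medications allows oral prednisone up to 20 mg/day, azathioprine and methotrexate. Section 12 calls the infection risk minimal because of donor screening.

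**The concern.** Criterion 10 covers presence as well as history. A donor may carry an infection without knowing it, and an interview or questionnaire cannot reveal what the donor does not know. For HIV and hepatitis the plan backs the exclusion with a laboratory test. For HTLV it lists none, so its own exclusion cannot be applied to an undiagnosed carrier. Section 12 rests its low infection risk on this screening, the material is infused fresh, and some recipients will be immunosuppressed.

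The lesser matter is timing. Eligibility under a look-back criterion can change after screening, through a course of antibiotics, a trip or a new exposure. The plan does not describe how such a change would be noticed before the donor gives stool. That bears on safety. It also bears on the comparison of donors, because antibiotics, probiotics and proton pump inhibitors are among the plan's own donor exclusions.

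**Working it through.** The plan gives no figure to reproduce on this point. The check is a comparison of lists and a count.

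**Step 1. Infections named in criterion 10 against tests listed in criterion 49.**

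| Infection in criterion 10 | Listed test |
|---|---|
| HIV | HIV |
| Hepatitis B | Hepatitis panel |
| Hepatitis C | Hepatitis panel |
| HTLV | None |

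Three of the four have a listed test. Syphilis, which criterion 42 names alongside HTLV, also has one. Two assumptions are made because the panels are not itemised: that the hepatitis panel covers B and C, and that Torch 5 does not include HTLV.

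**Step 2. Follow an undiagnosed HTLV carrier through the described steps.**

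- Interview and questionnaire: the donor has no known history to report.
- Criterion 42: this excludes the donor only if a partner was confirmed positive, the contact was within 12 months, and the donor knows and reports it.
- Criteria 32 and 35 to 41 (injection drug use, sexual risk, sexually transmitted infection): these exclude some carriers indirectly, but not one with no such history.
- Criterion 49: no listed assay is directed at HTLV.

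Unless something else excludes the donor, the donor is accepted.

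**Step 3. Count the relative look-backs among the donor exclusions.**

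| Window | Criteria | Number |
|---|---|---|
| 1 month | 30 | 1 |
| 2 months | 6, 28, 29, 31 | 4 |
| 6 months | 9, 43, 44 | 3 |
| 12 months | 37 to 42 | 6 |

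Total: 1 + 4 + 3 + 6 = 14. Criterion 8 uses fixed calendar years (1980 to 1996) and is not counted. Of the 14, nine concern exposures that bear on infection (9 and 37 to 44: 1 + 8 = 9). Five concern medicines, probiotics, vaccines or trial products (6 and 28 to 31: 1 + 4 = 5).

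**Step 4. Look for a check at donation.** Screening is described once, without timing. Neither the donor section nor any other part of the document describes a repeat questionnaire, a repeat test, a period for which screening stays valid, or a check on the day of donation.

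**Step 5. Scale.** 100 recipients × 3 infusions = up to 300 infusions. The plan gives no number of donors, donations per donor, interval from screening to donation, or HTLV prevalence. The count of affected donations cannot be taken further.

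**The case against.** **On HTLV.** Criterion 10 ends by referring to other known infections, so it can be read as a known-status criterion, in which case a missing assay is not a contradiction. The behavioural exclusions also remove some donors at risk. Whether stool donors need HTLV serology depends on prevalence and donor-screening standards, and the documents give neither. This stands as far as size is concerned: no harm can be quantified. It does not remove the gap, because the criterion names presence and the plan tests for the other three infections in the same line. A reader might go further and infer that the HTLV exclusion depends on the donor's history alone. That is less exact than the text allows, since the criterion covers presence too. What the documents support is that no HTLV test is listed.

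**On timing.** A reader might infer that the plan lets a donor who became ineligible after screening give stool. The collection rule says otherwise: its natural reading is that a donor who took antibiotics last week does not meet criterion 28 and may not donate. Nor does the plan say that screening happens once only; it is silent, and donor handling may be set out in a procedure outside this document. What remains is that no confirming step is written down.

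**On comparison with recipients.** A reader might contrast the undated donor windows with recipient criterion 12, where all six drug windows have a reference point, for example "Probiotics within 4 weeks before the first FMT" and "Other major immunosuppressants (e.g., calcineurin inhibitors, antitumor drugs) within 12 weeks prior to treatment". The contrast is selective. Recipient criteria 9 (appendectomy) and 10 (antibiotics) also give a window without a reference date, so 6 of 8 recipient windows are anchored. Recipient criterion 10 is the direct counterpart of donor criterion 28 and is phrased in the same way, although the Prohibited Medications list later ties antibiotics to the study period. No weight is placed on this contrast.

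**Conclusion.** The HTLV point holds. The plan excludes the presence of an infection for which it lists no test, and it does list tests for the other three infections in that criterion. Followed as written, it cannot identify an undiagnosed carrier whom its own exclusion bars. This rests on the plan's own criteria, not on an outside standard, and on the assumption that Torch 5 does not cover HTLV. The case for change is that the remedy is cheap, not that harm has been shown. The documents give no prevalence, no donor count and no probability of transmission by stool, and the number of affected donations may be zero.

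The timing point is secondary and minor. The eligibility rule is sound; what is missing is operational detail on how 14 time-limited criteria are confirmed at donation.

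Neither point touches sample size, power, significance level or the analysis.

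**What to change.** 1. **Main change.** Add HTLV serology to the blood tests in donor criterion 49. Cost: one extra assay per donor on blood already drawn, and an occasional excluded donor.
2. **Minor clarification.** State that the 14 time-limited donor criteria (6, 9, 28 to 31, 37 to 44) are counted back from each donation date. Re-ask the existing questionnaire at each donation and discard a donation that fails. Cost: a few minutes per donation, and an occasional discarded donation or delayed infusion. Limit: this finds only changes that the donor reports, not new silent infection or carriage.

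The two changes are independent, and either can be adopted without the other. If a separate donor procedure already covers the second, a reference to it in the donor section is enough.

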## **5. Study Process:**

## Groups

Groups	Fresh fecal bacterial solution (Ethnic Han Donor)	Fresh fecal bacterial solution (Bai Ethnic Donor)
Planned enrollment	50 Patients	50 Patients
Planned completed 12-week follow-up	30 Patients	30 Patients

### 1.FMT:

Fresh fecal bacterial solution was obtained through the fecal bacterial transplantation isolation system (FMT-6A-50/12-AS, Nanjing), which was directly infused into the ileocecal region through the TET tube of colonoscopy within 30 minutes, 100 mL each time. The fresh fecal bacterial solution was given at an interval of one day for a total of 3 transplantations.

### 2.Mayo Score:

The Mayo score is calculated according to Table 1, with clinical remission defined as a total Mayo score  $\leq 2$  and no individual subscore  $>1$ .

Table 1 Mayo Score

Item	Score	Evaluation
1. Stool frequency a	0	Normal number of stools
	1	1-2 more than normal
	2	3-4 more than normal
	3	$\geq 5$ more than normal
2. Rectal bleeding b	0	No blood seen
	1	Streaks of blood with stool in in less than half of the cases
	2	Obvious blood with stools in most of the time
	3	Blood alone passed
3. Endoscopic findings	0	Normal mucosa or inactive disease
	1	Mild activity (erythema, decreased vascular pattern, mild friability)
	2	Moderate activity (marked erythema, lack of vascular pattern, friability, erosions)
	3	Severe activity (spontaneous bleeding, large ulcerations)
4. Physician's global assessment	0	Normal c
	1	Mild disease d
	2	Moderate disease e
	3	Severe disease f

a Each patient serves as their own control to establish the degree of abnormal stool frequency.

b The daily rectal bleeding score represents the most severe bleeding observed on a single day.

c No symptoms of colitis; the patient feels well, with a flexible sigmoidoscopy score of 0.

d Mild symptoms with mild abnormalities observed on sigmoidoscopy; primarily scored as 1.

e More severe abnormalities, with sigmoidoscopy and symptom scores between 1 and 2.

f Sigmoidoscopy and symptom scores of 2 to 3, where the patient may require corticosteroid treatment and hospitalization.

Note: A score of  $\leq 2$ , with no individual subscore  $>1$ , indicates clinical remission. A score of 3 – 5 indicates mild activity, 6 – 10 indicates moderate activity, and 11 – 12 indicates severe activity.

